9.4.20 FACIT-Fatigue Questionnaire (FACIT-F)

The FACIT Fatigue Questionnaire is a 13-item tool that measures an individual's level of fatigue during their usual daily activities over the past week. The level of fatigue is measured on a four point scale (4 = not at all fatigued to 0 = very much fatigued). The Fatigue scale ranges from 0 to 52, with higher scores indicating less fatigue.

Item score for each item is calculated by either subtracting from 4 or adding 0 depending on whether it is a reversal item or not. FACIT Fatigue is then calculated by adding up all item scores, multiplying by 13 and dividing by the number of items answered. If less than 7 items are answered, the scale will not be computed.

9.4.21 EuroQoL-5D (EQ-5D-5L)

EQ-5D measures 5 dimensions of health status (mobility, self-care, usual activities, pain/discomfort, and anxiety/depression) with 5 levels per dimension (no problems, slight problems, moderate problems, severe problems, and extreme problems corresponding to Level 1 to Level 5 respectively) and includes the EQ Visual Analogue Scale (EQ VAS).

The 5 dimensions of health status are converted into a single index value. The change from baseline of the index value and the EQ VAS will be analyzed and reported. UK scoring algorithm will be used.

9.4.22 Form SF-36v2

The 36-Item Short Form, Version 2 (SF-36v2) health survey consists of 36 general health questions. It has 2 components: physical and mental. For each component, a transformed summary score is calculated using 8 sub domains: physical functioning, role-physical, bodily pain, general health, vitality, social functioning, role-emotional, and mental health.

The coding and scoring for the SF-36 will use the software provided by QualityMetrics.

9.4.23 Work Productivity and Activity Impairment Questionnaire Psoriatic Arthritis (WPAI)

The Work Productivity and Activity Impairment Questionnaire: Psoriatic Arthritis, V2.0 (WPAI) measures the effect of overall health and specific symptoms on productivity at work and outside of work. It consists of 6 questions. A lower WPAI score indicates an improvement. The WPAI is collected at the designated study visits listed in the protocol. The WPAI coding and scoring methods are described in the following:

The 6 measures will be derived based on the responses from the 6 questions. The 4 main impairment scores (S1 to S4) are expressed as *percent impairment* based on the 6 questions.

Scores:

- S0. Employment: defined below in missing data handling conventions
- S1. Absenteeism: Percent work time missed due to PsA:

$$100 \times \left[\frac{Q2}{Q2 + Q4} \right]$$

S2. Presenteeism: Percent impairment while working due to PsA:

$$100 \times \left\lceil \frac{Q5}{10} \right\rceil$$

S3. Percent overall work impairment due to PsA:

$$100 \times \left[\frac{Q2}{Q2 + Q4} + \left\{ 1 - \frac{Q2}{Q2 + Q4} \right\} \times \frac{Q5}{10} \right]$$

S4. Percent activity impairment due to PsA:

$$100 \times \left[\frac{Q6}{10} \right]$$

S5. Did subject miss work (defined below). This is needed to derive the proportion of subjects who missed work.

Missing Data Handling Conventions

When calculating the WPAI: PsA scores, the following computational notes should be followed.

- Define Employment as a binary YES or NO variable where YES corresponds to "Employed" and NO corresponds to "Not Employed."
 - A subject will be considered "employed" at a given visit if Q1 = YES or Q2 > 0 or Q4 > 0.
 - A subject will be considered "unemployed" at a given visit if Q1 = NO and no positive hours recorded under Q2 and Q4 (i.e., if Q1 = NO AND Q2 ≤ 0 AND Q4 ≤ 0, then UNEMPLOYED).
 - Employment status for a subject will be considered "missing" at a given visit if Q1 = missing and no positive hours recorded under Q2 and Q4.
- If a subject is "unemployed" or employment status is "missing," then S1, S2, and S3 will be set to "missing."

[figure not shown]
- If Q2 = 0 and Q4 = 0 are missing then Q2/(Q2 + Q4) = missing (i.e., S1 = missing).
- If Q2 = 0 and Q4 = 0, then set S3 to missing.
- If Q2 is missing or Q4 is missing, then set S1 and S3 to missing.
- If Q4 = missing, then DO NOT set Q5 = missing.
- If Q5 is missing, then apply the following rules:
 - \circ If Q2 > 0, Q4 = 0, and Q5 = missing, then S3 = 100%.
 - \circ If Q2 = 0, Q4 > 0, and Q5 = missing, then S3 is missing.
 - \circ If Q2 > 0, Q4 > 0, and Q5 = missing, then S3 is missing.
- Determine if a subject missed work (based on Q2) in order to analyze the proportion of subjects who missed work:
 - Create a binary (yes or no) "missed work" variable.
 - A subject will be considered as yes to missed work if Q2 is greater than 0.
 - If Q2 = missing, then MISSED WORK = missing.
 - \circ If Q2 > 0, then MISSED WORK = "yes."
 - o If Q2 = 0, then MISSED WORK = "no."

Therefore, the proportion of subjects who missed work will be counted based on the number of subjects with MISSED WORK = YES.

9.4.24 Health Resource Utilization (HRU) Questionnaire

The HRU questionnaire contains three questions regarding health care utilization in the following categories: unscheduled health care professional visits, emergency room visits, and hospital admissions. The data gathered from the HRU questionnaire will be used to calculate the individual cumulative number of utilizations per time (e.g., subject-year) under observation in each variable (i.e., the number of unscheduled PsA-related health care professional visits, the number of emergency room visits, the number of hospital admissions and the total number of days in hospital) as follows:

• Time under observation for a subject will be defined as "date of last visit with non-missing HRU – date of baseline visit."

• The number of utilizations after baseline will be summed up for each subject.

To determine cumulative HRU over all subjects, the ratio of the total number of utilizations (i.e., over all subjects) and the total time under observation (i.e., over all subjects) will be calculated across all subjects in each treatment group. HRU will be analyzed as observed only.

9.4.25 Modified PsA Sharp/van der Heijde Score (SHS)

Radiographic outcomes will be assessed and scored according to Sharp's method (van der Heijde modification for PsA) centrally by two qualified readers who will be blinded to site number, subject number, treatment allocation, time sequence and clinical response.

Calculation of the SHS Score

To obtain the total SHS score, scores for erosions and JSN in both the hands and feet will be added together.

The following considerations are applied before score summation:

- Osteolysis in the form of pencil-in-cup: Osteolysis of the proximal phalanx and the base of the distal phalanx resulting in a pencil like proximal phalanx covered by cup like base of the distal phalanx. Pencil-in-cup will be scored as "P" where applicable.
- Gross Osteolysis: Osteolysis of the phalanx resulting in a loss of the normal joint structure, usually accompanied by shortening of the length of the phalanx. Gross osteolysis will be scored as "G" where applicable.

For the purpose of summing total scores, "G" or "P" assigned by the IRC reviewers will be associated with a maximum score per feature (JSN and erosion score) per location in analyses of radiographic scores.

Not Visible and Surgically Modified Joints/Bones

If a joint or bone is not visible (e.g., poor film quality, missing imaging, severe misalignment, flexion deformity, dislocation) at the timepoint, the individual joint or bone will be coded as Not Visible (N). If radiographs at the timepoint show a joint or bone with surgical fusion, replacement (prosthesis), or amputation, then the joint or bone will be scored Surgically Modified (S).

For joints and bones with end stage disease, scores N and S should not be used.

The range of scores is summarized below.

Table 10. Range of Total SHS Score, Erosion Score and Joint Space Narrowing

	Hands	Feet	Total (Hands and Feet)
Erosion Score Range	0 - 200	0 - 120	0 - 320
Joint Space Narrowing Range	0 - 160	0 - 48	0 - 208
Total SHS Range for Erosion and JSN	0 - 360	0 - 168	0 - 528

Erosion Assessment

Erosions will be assessed in each hand (20 locations per hand) and foot (6 locations per foot). The locations assessed in the SHS method include:

Hands:

- 4 Distal inter-phalangeal joints (2 5)
- 5 Metacarpo-Phalangeal Joints (1 5)
- 4 Proximal Inter-Phalangeal Joints (2 5)
- Inter-Phalangeal Joint of the thumb
- Proximal first Metacarpal Bone
- Radius Bone

- Ulnar Bone
- Trapezium and Trapezoid (as one unit; multangular)
- Navicular Bone
- Lunate Bone

Feet:

- 5 Metatarso-phalangeal joints (1 5)
- Inter-phalangeal joint of the first toe

Joint Space Narrowing Assessment

Joint space narrowing (JSN) will be assessed in each hand (20 locations per hand) and foot (6 locations per foot). The locations assessed in the SHS method include:

- Hand Joints:
 - o 4 Distal inter-phalangeal joints (2 5)
 - 4 Proximal inter-phalangeal joints (2 5)
 - 5 Metacarpo-phalangeal joints (1 5)
 - Interphalangeal Joint of thumb (IP)
 - o 3 Carpo-metacarpal joints (3 5)
 - o Radio-carpal joint
 - o Multangular-navicular joint
 - o Capitate-navicular-lunate joint
- Foot Joints:
 - o 5 Metatarso-phalangeal joints
 - Inter-phalangeal joint of first toe

For each Joint and Bone assessed, scores range as follows:

• Erosions: 0-5 (hands/wrists) or 0-10 (feet) to characterize the extent of erosions (where 0 denotes no erosion).

 Joint Space Narrowing: 0 − 4 to characterize the extent of Joint Space Narrowing (JSN) (where 0 denotes no narrowing).

Erosion and JSN scores for each reader are calculated by taking the sum of the left and right joints as shown below.

$$Erosion_{Readeri} = Erosion_{Left} + Erosion_{Right}$$

$$JSN_{Readeri} = JSN_{Left} + JSN_{Right}$$

for i = 1, 2.

Thus, the maximum erosion score for the hands is 200. The maximum erosion score for the feet is 120. Thus, the total erosion score for hands/wrists and feet is 320.

The maximum score for JSN in all 40 hand joints is 160. The maximum score for JSN in all 12 feet joints is 48. Thus, the total JSN score for hand and feet is 208.

Since two independent readers evaluate each film, the mean score will be calculated for the two readers from the individual erosion and JSN scores as shown below:

$$Joint Erosion = \frac{Erosion_{Reader1} + Erosion_{Reader2}}{2}$$

$$JSN = \frac{JSN_{Reader1} + JSN_{Reader2}}{2}$$

The SHS for each reader is defined as the sum of the erosion and JSN scores:

$$SHS_{Reader i} = Erosion_{Reader i} + JSN_{Reader i}$$
 for $i = 1, 2$.

The average modified SHS from the two readers will be used for all x-ray endpoint calculations.

$$SHS = \frac{SHS_{reader1} + SHS_{reader2}}{2}$$

Handling of Missing Joints in the SHS Derivation

[figure not shown]
If a score at any location/joint is missing, the method described below will be used for deriving SHS.

- If the score for a location/joint is missing at Baseline, this joint will not contribute to the calculation of SHS for this subject at any visit within the reading session (even if the score for this location/joint is available at post-baseline visits).
- If the score for a location/joint is missing at all post-baseline visits within a reading session, this joint will not contribute to the calculation of SHS for this subject at any visit within the reading session (even if the score for this location/joint is available at Baseline).
- If the score for a location/joint is available at Baseline and at least one post-baseline visit, missing scores for this joint at any other post-baseline visit will be imputed assuming no progression from the previous time point with available score.

Adjudication Process

Two reviewers will independently review the images. Adjudication will occur for all subjects with a discrepancy of $\geq |8$ units | between the two reviewers' SHS change scores, in which case another reviewer, different from the reviewers who performed primary assessments, will make a third, independent assessment.

For the calculation of SHS, the score of two closest reads (out of the two primary reviewers and the adjudicator) will be used. In the case of equal distance, the average of the three reads will be used.

10.0 Safety Analysis

10.1 General Considerations

Safety analyses will be carried out using the Safety Analysis Set by "as treated" treatment groups. There are two sets of planned safety analysis: safety analysis by Week 24, and long-term safety analysis.

Safety Analysis through Week 24

Standard safety analysis by the "as treated" treatment groups of upadacitinib 15 mg QD, upadacitinib 30 mg QD, adalimumab 40 mg EOW and combined placebo groups will be performed on safety data up to Week 24. No protocol-defined treatment switching will occur prior to this time point.

The standard safety analyses will include reporting of adverse events (AEs), laboratory, and vital signs measurements. Frequency tables of subjects with treatment-emergent adverse events (TEAEs) by system organ class (SOC) and by preferred term (PT) as in the Medical Dictionary for Regulatory Activities (MedDRA) dictionary will be provided by as-treated treatment groups. Mean changes from baseline in all continuous laboratory parameters and vital signs variables at each visit will be summarized by "as treated" treatment groups. Frequency tables of subjects meeting criteria for potentially clinically significant vital sign values and for potentially clinically significant laboratory values will be provided by as-treated treatment groups. Missing safety data will not be imputed. Treatment comparison of upadacitinib versus placebo and ADA will be provided for key safety endpoints including overview of AE, overview of AE of special interest, change from baseline in selected laboratory parameters, and potentially clinically significant laboratory values. Treatment difference and corresponding 95% CI will be provided.

Long-Term Safety Analysis

[figure not shown]
Long-term safety analyses that account for protocol-defined treatment switching include reporting of AE rate adjusted by cumulative exposure, descriptive summary in laboratory parameters and vital sign variables by visit, and rate of potentially clinically significant laboratory and vital signs values. The treatment-emergent adverse event (TEAE) rate per 100 patient-years of exposure will be presented by actual treatment received at the time of AE (as described in Section 10.2.2). Listing of subjects with TEAEs by SOC and PT will be provided. Summary statistics for laboratory parameters and vital signs variables at each visit will be presented by "as treated" treatment group sequences defined below. Frequency tables and listings of subjects meeting criteria for potentially clinically significant vital sign values and for potentially clinically significant laboratory values will be provided by actual treatment received at the time of event. Missing safety data will not be imputed.

"As treated" treatment group sequences are defined as follows:

- 1. Placebo → Upadacitinib 15 mg QD
- 2. Placebo → Upadacitinib 30 mg QD
- 3. Upadacitinib 15 mg QD
- 4. Upadacitinib 30 mg QD
- 5. Adalimumab 40 mg EOW

Starting with Amendment 6.01 (for Japan) and Amendment 7 and 7.01(for global), subjects receiving upadacitinib 30 mg QD will be switched to upadacitinib 15 mg QD. For these subjects, adverse events and exposure to upadacitinib 30 mg QD will be censored at the time of dose switch; subsequent adverse events and exposure starting the day of first dose of upadacitinib 15 mg QD will be summarized under separate groups, as described in Section 8.2.

Assessment of potentially clinically significant laboratory and vital sign values will be based on the same treatment groups as for adverse events. The baseline value for PCS determination will be the last non-missing value collected before the first dose of UPA (regardless of dose).

For descriptive summary by visit or mean change from baseline in laboratory values and vital signs, exposure sequences 2 and 4 (i.e., subjects who switched from upadacitinib 30 mg QD to 15 mg QD) will be censored at the time of dose switch. Descriptive summary by visit or mean change from baseline for laboratory values and vital signs collected after dose switch will be summarized separately by visits post switch. Note for analysis of mean change from baseline in laboratory values, the study baseline is used.

Treatment comparisons of upadacitinib versus ADA will be provided for key safety endpoints including overview of AE, overview of AESI, selected lab parameters, and potentially clinically significant laboratory values. Treatment difference and corresponding 95% CI will be provided.

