8.0 Study Drug Exposure and Compliance

8.1 Study Drug Exposure

For short term up to Week 24, the duration of exposure to study drug will be summarized for the safety analysis set by the randomized treatment groups.

For long term, the duration of exposure to study drug will be summarized for the safety analysis set by the following groups.

1. Upadacitinib 15 mg QD

This includes upadacitinib 15 mg QD exposure from subjects starting on upadacitinib 15 mg QD and subjects switching from placebo to upadacitinib 15 mg QD.

2. Upadacitinib 30 mg QD

This includes upadacitinib 30 mg QD exposure from subjects starting on upadacitinib 30 mg QD and subjects switching from placebo to upadacitinib 30 mg QD. Exposure is censored at time of dose switch from upadacitinib 30 mg QD to upadacitinib 15 mg QD.

3. Upadacitinib 15 mg QD switched from upadacitinib 30mg QD

This includes Upadacitinib 15 mg QD exposure from subjects who switched dose from upadacitinib 30 mg QD to upadacitinib 15 mg QD.

4. Adalimumab 40 mg EOW

Exposure to upadacitinib and placebo is defined as last dose date minus first dose date plus 1 day. Exposure to adalimumab is defined as last dose date minus first dose date plus 14 days.

Starting with Amendment 6.01 (for Japan) and Amendment 7 and 7.01(for global), subjects receiving upadacitinib 30 mg QD will be switched to receiving upadacitinib 15

mg QD. Exposure to upadacitinib 30 mg QD (Groups 2) will be censored prior to the day subject received the first dose of upadacitinib 15 mg QD, and subsequent exposure to upadacitinib 15 mg QD will be summarized under separate groups (Groups 3).

The duration of exposure to study drug will be summarized for each group as specified above, with the number of subjects, mean, standard deviation, median, minimum and maximum values. In addition, the number and percentage of subjects exposed to study drug will be summarized for the following cumulative duration intervals.

- ≥ 2 weeks
- ≥ 1 month
- \geq 3 months
- \geq 6 months
- ≥ 9 months
- ≥ 12 months
- ≥ 18 months
- ≥ 2 years
- ≥ 2.5 years
- ≥ 3 years
- ≥ 3.5 years
- \geq 4 years
- ≥ 4.5 years

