- Change from baseline in SHS
- Change from baseline in joint space narrowing score and joint erosion score
- Proportion of subjects with no radiographic progression (defined as change from baseline in SHS ≤ 0);

Descriptive statistics based on AO will be provided for each randomized treatment group sequence as defined in Section 9.1.1. These include the number of observations, mean, standard deviation, 95% CI, median, minimum and maximum for continuous endpoints; and frequencies and percentages with 95% CI using normal approximation for binary endpoints. Plot for each randomized treatment group sequence over time will be provided for key endpoints. Additionally, treatment comparisons between each upadacitinib dose versus adalimumab will be made for efficacy endpoints for the originally randomized upadacitinib groups and adalimumab group. Point estimate, nominal p value and 95% CI will be provided up to Week 56. Treatment comparisons may also be provided after Week 56 as appropriate.

In addition, NRI approach and/or GLMM will be used for non-radiographic binary endpoint analysis, and MMRM will be used for continuous endpoint analysis. The analyses will be performed for the treatment sequences. The longitudinal analysis using MMRM or GLMM was described in Section 9.1.2. Point estimates and 95% CI from the model will be provided for each treatment sequence. Plot for each randomized treatment group sequence over time will be provided for key endpoints.

For radiographic related endpoints, the analysis will be based on linear extrapolation imputation and AO data. MMRM described in Section 9.1.2 will be conducted as mixed model based on AO data for Week 104 and future analyses.

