10.2.2 Analysis of Long-Term Adverse Event Rates

Long-term adverse events will be analyzed using event rates adjusted by cumulative exposure and will be based on the actual treatment received at the time of AE occurrence. For subjects switched from upadacitinib 30 mg QD to upadacitinib 15 mg QD, adverse events and exposure to upadacitinib 30 mg QD will be censored at the time of dose switch; subsequent adverse events and exposure starting the day of first dose of upadacitinib 15 mg QD will be summarized under separate groups. The detailed treatment groups including the handling of dose switch, are described in Section 8.1.

Exposure-Adjusted Event Rate (EAER)

To adjust for potentially different follow-up time between treatment groups, EAER will be provided. For the purpose of event rate calculation, the numerator will be the total number of AEs reported for the event (i.e., a subject can contribute more than one event to the numerator) and the denominator will be the total exposure time among subjects under the treatment group. The number of AEs reported (numerator), the total number of years of study drug exposure (denominator), and the exposure-adjusted AE event rate per 100 patient-years, calculated as ([numerator/denominator])*100, will be presented for each treatment group. The EAER will be the main approach to evaluate AEs in the long-term analysis.

The exposure adjusted incidence rate (censored at the time of first event) may be conducted for selected AESI endpoints as appropriate for long-term analysis.

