10.3.2.4 Assessment of Liver Elevations

According to FDA's Guidance for Industry "Drug-Induced Liver Injury: Premarketing clinical evaluation" (July 2009), when aminotransferase (AT) abnormalities indicating hepatocellular injury are accompanied by evidence of impaired hepatic function (bilirubin elevation > 2 × ULN), in the absence of evidence of biliary obstruction (i.e., significant elevation of ALP) or some other explanation of the injury (e.g., viral hepatitis, alcohol hepatitis), the combined finding (i.e., Hy's Law cases) represents a signal of a potential for the drug to cause severe DILI.

For the purpose of assessing for potential Hy's law cases, the frequencies and percentages of subjects with post baseline liver specific function test values that meet the following criteria of potential clinical interest will be summarized by treatment groups:

- ALT \geq 3 × ULN
- ALT \geq 5 × ULN
- ALT $\geq 10 \times ULN$
- ALT $\geq 20 \times ULN$
- AST \geq 3 × ULN
- AST \geq 5 × ULN
- AST $> 10 \times ULN$

- $AST > 20 \times ULN$
- TBL \geq 2 × ULN
- Alkaline phosphatase $\geq 1.5 \times ULN$
- ALT and/or AST \geq 3 × ULN and concurrent TBL \geq 1.5 × ULN
- ALT and/or AST \geq 3 × ULN and concurrent TBL \geq 2 × ULN

10.3.3 **Analysis of Long-Term Laboratory Data**

10.3.3.1 **Assessment of Clinical Laboratory Variables**

[figure not shown]
Analyses of hematology, chemistry, and urinalysis variables which are measured longitudinally will be performed by visits and by treatment group sequences as described in Section 10.1. For each analysis, the following summary statistics of visit values will be presented for each treatment group sequence: sample size, mean, standard deviation, minimum, median and maximum.

Analyses will be performed for change from baseline in hemoglobin, lymphocytes, neutrophils, creatinine, and creatine phosphokinase (CPK).

Descriptive summary by visit or mean change from baseline in laboratory values for subjects who switched from upadacitinib 30 mg QD to 15 mg QD will be censored at the time of dose switch, and descriptive summary by visit or mean change from baseline for values post switch will be summarized separately, as described in Section 10.1.

10.3.3.2 **Assessment of Potentially Clinical Significant Laboratory Values**

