Long-term laboratory data will be summarized based on the number and percentage of subjects meeting the criteria for potentially clinical significant laboratory values and by the actual treatment received at the time of the event occurrence. The treatment groups for summarizing potentially clinically significant laboratory values are the same as the ones for long-term AE analysis as described in Section 8.1.

A subject can be counted under different treatment groups if he/she was on placebo from baseline to Week 24 and then started upadacitinib 15 or 30 mg at Week 24 and experienced potentially clinical significant laboratory values under different treatment groups.

[figure not shown]
In the evaluation of potentially clinically significant laboratory values, the baseline value will be determined by the last non-missing measurement recorded on or before the date of the first dose of study drug in the corresponding treatment group (which may be different than the first dose of study drug received in the study). For example, for a subject who started on placebo and switched to upadacitinib 15 mg QD at Week 24, lab values under upadacitinib 15 mg QD exposure would be evaluated against the baseline value defined as the last non-missing measurement recorded on or before the date of the first dose of upadacitinib 15 mg QD. For subjects who switched from upadacitinib 30 mg QD to upadacitinib 15 mg QD, lab values under upadacitinib 15 mg QD exposure would still be evaluated against the baseline defined based on the first dose of Upadacitinib 30 mg QD.

A listing of all subjects with any laboratory determination meeting CTCAE criteria of Grade 3 or above with a grade worsening compared to baseline will be provided. For each of these subjects, the whole course of the respective parameter will be listed.

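### The long-term adverse event, AESI and PCS laboratory comparisons with adalimumab use upadacitinib groups that include Week 24 placebo crossovers and 30 mg time cut at the dose switch, so they are partly non-randomised and, for 30 mg, not same-period

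*SAP*

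**What the plan says.** SAP Section 10.1 (Long-Term Safety Analysis) promises: "Treatment comparisons of upadacitinib versus ADA will be provided for key safety endpoints including overview of AE, overview of AESI, selected lab parameters". PCS laboratory values are also included, and a difference with a 95% CI is to accompany each comparison. The sentence does not define the upadacitinib group.

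The groups come from other sections. For long-term AE rates, Section 10.2.2 says: "The detailed treatment groups including the handling of dose switch, are described in Section 8.1". For PCS laboratory values, Section 10.3.3.2 says the groups "are the same as the ones for long-term AE analysis as described in Section 8.1". In Section 8.1 the 15 mg group is the exposure of "subjects starting on upadacitinib 15 mg QD and subjects switching from placebo to upadacitinib 15 mg QD". The 30 mg group is that of "subjects starting on upadacitinib 30 mg QD and subjects switching from placebo to upadacitinib 30 mg QD", censored when the subject moves to 15 mg. Time after that move is a separate group. Adalimumab is one group with no delayed starters and no matching cut.

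Two other parts of the SAP are built differently. Long-term laboratory values by visit "will be performed by visits and by treatment group sequences as described in Section 10.1" (Section 10.3.3.1), and there the placebo crossovers are separate rows. Long-term efficacy comparisons with adalimumab are made "for the originally randomized upadacitinib groups and adalimumab group" (Section 9.3; Section 9.1.1 names sequences 3, 4 and 5).

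**The concern.** Comparing safety with adalimumab is part of a stated secondary objective. A crossover contributes upadacitinib time only if still on study drug at Week 24. Crossovers start 24 weeks after randomisation, some after rescue from Week 16, and have no adalimumab counterpart. For PCS values their baseline is taken before the first upadacitinib dose, at about Week 24, whereas for adalimumab it is Day 1.

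The 30 mg cut adds a second mismatch. Time on 30 mg ends at the amendment-driven switch, while adalimumab may continue to Week 260. The 30 mg rate therefore carries more early time on drug and less time after 1 February 2020, the date from which Appendix F counts COVID-19 events.

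Dividing by exposure corrects for length of follow-up, but not for who is followed or when. Section 10.3.3.2 reports PCS values as numbers and percentages of subjects, so there even length is not corrected. Two drugs with the same risk over time could show a difference.

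**Working it through.** **Inputs from the documents.** 1640 subjects at 2:2:2:1:1 give 1640 × 2/8 = 410 per active arm and 1640 × 1/8 = 205 per placebo sequence, matching SAP Section 4.2. Crossover is at Week 24 and follow-up runs to Week 260. The SAP states no precision for this comparison, so there is no planned figure to reproduce.

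**Assumptions.** Placebo loss before Week 24 is 10% (the planning dropout rate), so 205 × 0.9 = 184.5 crossovers per dose. There is no other dropout. Both drugs have the same true rate pattern, with the first 24 weeks at r times the later rate (r = 1.5, 2, 3).

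**Share of crossovers.** Subjects: 184.5/594.5 = 31%. Person-weeks to week T: 410T for randomised subjects and 184.5(T − 24) for crossovers.
- Week 104: 14,760/(42,640 + 14,760) = 26%
- Week 260: 43,542/(106,600 + 43,542) = 29%

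With 0% or 20% placebo loss the Week 260 share is 31% or 27%.

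**Effect of pooling, 15 mg.** The rate for adalimumab, or for upadacitinib as randomised, is 1 + (r − 1) × 24/T. The pooled rate is:
- if risk follows time on drug: 1 + (r − 1) × 24 × 594.5/(pooled person-weeks)
- if risk follows study time: 1 + (r − 1) × 24 × 410/(pooled person-weeks)

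Example, Week 104, r = 2: 1.2486/1.2308 = 1.014 (time on drug); 1.1714/1.2308 = 0.952 (study time).

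| Pooled 15 mg / adalimumab | r = 1.5 | r = 2 | r = 3 |
|---|---|---|---|
| Week 104, time on drug | 1.008 | 1.014 | 1.024 |
| Week 260, time on drug | 1.001 | 1.002 | 1.005 |
| Week 104, study time | 0.973 | 0.952 | 0.919 |
| Week 260, study time | 0.987 | 0.975 | 0.955 |

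The true ratio is 1.000 throughout. Both the sign and the size depend on the time scale.

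**Effect of the uncut adalimumab time, 30 mg.** Take only subjects randomised to 30 mg, switched at an assumed Week 130, against adalimumab to Week 260, with r = 2:
- 30 mg: (48 + 106)/130 = 154/130 = 1.185
- adalimumab: (48 + 236)/260 = 284/260 = 1.092
- ratio 1.085, an excess of about 8.5% with no crossovers involved

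Adding crossovers on the time-on-drug scale: (410 × 154 + 184.5 × 130)/(410 × 130 + 184.5 × 106) = 87,125/72,857 = 1.196, and 1.196/1.092 = 1.095. Pooling thus adds about 1 point.

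Range for the 8.5%, by the same formula:
- r = 1.5 or 3 at Week 130: 4.4% or 15.6%
- r = 2 with a switch at Week 104 or 152: 12.7% or 6.0%
- r = 2, switch at Week 130, adalimumab data only to Week 152: 1.185/(176/152) = 1.023, or 2.3%

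**Calendar time.** Assume randomisation on 1 July 2018 and a switch on 1 June 2021, which is 1,066 days or about Week 152. Time on 30 mg after 1 February 2020 is 486/1,066 = 46%. For adalimumab to Week 260 (1,820 days) it is (1,820 − 580)/1,820 = 68%.

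**The case against.** Several points on the other side stand.

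- A reader might infer that the trial gives up its randomised safety comparison with adalimumab. It does not. Section 10.1 plans one through Week 24, covering AEs, AESIs, selected laboratory changes and PCS values, with differences and CIs.
- A reader might extend the point to every long-term safety output. The by-visit laboratory parameters follow unpooled sequences and are not affected.
- A reader might apply it to Week 56 results. Section 11.1 says Period 1 reporting was completed under SAP version 3.0, which is not among the documents, and that the current version governs future long-term reporting only.
- A reader might infer that pooling inflates upadacitinib rates. The documents do not fix the direction, as the table shows.
- Calling the comparison simply non-randomised goes too far. About 69% of each pooled group (410/594.5) was randomised to that dose on Day 1. Crossovers were preassigned to their later dose at Baseline and switch regardless of response.
- As-treated pooling is a legitimate choice for long-term safety. It adds exposure for rare AESIs, so dropping it would trade bias for precision.

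What remains is that unnamed groups feed a between-drug difference with a CI, although an as-randomised version can be built from data already held. The precision argument does not cover the 30 mg mismatch, where the two sides are followed over different periods.

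**Conclusion.** The concern holds for the long-term AE overview, AESI overview and PCS laboratory values. Those upadacitinib-versus-adalimumab differences are partly non-randomised, and for 30 mg they are not same-period.

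For reporting still to come, the 15 mg distortion from pooling is modest: about +1-2% at Week 104 and under 1% at Week 260 if risk follows time on drug. If risk follows study time it is about −3% to −8% at Week 104 and −1% to −5% at Week 260. For 30 mg the uncut adalimumab time dominates: about 8.5% at a twofold early rate with a Week 130 switch, of a total of about 9.5% on the time-on-drug scale. Different exposure to the period after February 2020 comes on top.

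These sizes rest on assumed early-rate ratios, switch week, 10% placebo loss and no later dropout, none of which the documents settle for this comparison. They apply to exposure-adjusted event rates; the effect on PCS percentages was not quantified. This is a cheap improvement to the plan and does not invalidate the safety analysis.

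**What to change.** In SAP Section 10.1:

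1. Name the groups used for each long-term upadacitinib-versus-adalimumab safety comparison.
2. For the AE overview, AESI overview and PCS laboratory values, report differences and 95% CIs for the originally randomised sequences 3, 4 and 5, as in Sections 9.1.1 and 9.3, alongside the pooled Section 8.1 results.
3. For 30 mg versus adalimumab, censor each adalimumab subject in the analysis by the rule that ends 30 mg time: under Amendments 7 and 7.01, the first scheduled visit after approval; in Japan, the corresponding Amendment 6.01 switch timing. This is an analysis cut-off only. It needs the approval dates, which the documents do not give.
4. Tidy two related items. Section 10.1 points to Section 8.2 (which covers compliance) for the dose-switch groups, but they are in 8.1. Appendix E writes the rate-difference CI only against placebo, so an adalimumab version is needed.

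Cost: SAP wording, a subset flag and one extra set of tables. With equal rates, the randomised-only 15 mg CI is wider than the pooled one by √[(2/106,600)/(1/150,142 + 1/106,600)] = 1.081 at Week 260. The same formula gives 1.071 at Week 104 and 1.055 at Week 56, so about 6-8%. The 30 mg comparison also gives up adalimumab time. With a Week 130 cut on both sides, its CI is √[(2/53,300)/(1/72,857 + 1/106,600)] = 1.27 times the pooled, uncut one. The pooled tables stay as they are.
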